### Potential Limitations and Alternative Strategies for Aims 1 and 2.

False-positive associations will be controlled by our clearly defined analysis plan, the use of false-discovery rates to assess significance, and geneset/pathway analysis to maximize power and minimize false discovery. Statistical power to detect effects is driven by our sample size of 400 subjects, which is larger than most systems biology studies, including our prior study of SDFlu in older subjects where we and others were able to successfully identify transcriptomic signatures of vaccine response. Accumulation of information across multiple genes increases the percent of variability explained by the model and hence increases the likelihood of detecting effects. Our analysis approach will also test the association of each innate and Th cell immune response with the expression of all genes in a specified geneset using kernel methods. Advantages of kernel methods are the following: 1) they allow for correlations among the different genes in a geneset; 2) they are robust to when some genes are positively associated with a response, others are negatively associated with a response, and other genes in the geneset are not associated; 3) and they allow adjustment for covariates. Finally, we will evaluate data-driven genesets using WGCNA to group genes into biological modules, which is an approach we have successfully used (see Preliminary Data).

Separate mediation analyses will be performed for mRNA and miRNA. If we find both mRNA and miRNA to be separate mediators in our initial analyses, we will evaluate their joint effects as a pathway of mediators using techniques developed by VanderWeele. Other confounding factors (e.g., immunosenescence, underlying medical conditions, obesity, and CMV serostatus) will be evaluated in our analyses as potential confounders.

**Expected Results and Impact of Findings for Specific Aims 1 and 2.** Our publications and preliminary data indicate a high likelihood of identifying not only significant vaccine type-

and sex-specific differences in immune responses, but also transcriptomic signatures associated with those differences. Furthermore, the preliminary data from our mediation analysis support our hypothesis that changes in gene expression influence the effect of sex on immune response. We therefore anticipate identifying comparable sex-specific differences along with the genes/genesets mediating those responses (i.e., transcriptomic signatures), following receipt of MF59Flu and HDFlu. Pinpointing the innate and/or Th cell responses associated with humoral immunity to these vaccines facilitates our understanding of the critical pathways vaccines must trigger in order to elicit protective antibody titers.

Our data will also provide new insights into why men and women respond differently to influenza vaccines, and highlight the specific genetic pathways associated with MF59- and sex-based immune response differences.

Aims 1.1 and 2.1 may provide additional correlates of protection that can be used in conjunction with HAI titer to more accurately assess immune status. Understanding what genes and genesets are associated with the increased immunogenicity of MF59Flu and HDFlu (Aims 1.2 and 2.2) will inform functional studies verifying the mechanistic relationship between gene expression and immune function. For example, if TLR4 and TLR8 activation are strongly associated with increased APC activation and HAI titers, it suggests the use of a combination of GLA-SE (a TLR4 agonist) and CpG (a TLR8/9 agonist) might make an effective adjuvant. As another example, MF59 has been shown to enhance APC recruitment to the Ag site and transport of Ag to the draining lymph nodes. Due to reasons that are currently poorly understood, those processes are followed by enhanced Th cell responses and more robust (in terms of both titer and breadth of targets) Ab responses.

Evaluating the transcriptomic changes occurring in innate and Th cells after MF59Flu vaccination is likely to identify gene expression patterns occurring in the APCs and responding T cells, providing critical clues regarding the nature of the interactions between these cell types, and may highlight the receptor-ligand pairs and downstream signaling cascades responsible for enhanced T cell responses. Such information allows for directed and informed engineering of novel vaccine candidates and adjuvants. In the unlikely event that we do not identify vaccine type or sex-dependent differences, this finding will be interesting its own right, suggesting that further studies be conducted to find additional variables that do impact innate and/or Th responses to influenza A/H3N2.

### **Endpoints:**

Secreted cytokine levels

Detection of Functional Th Cell Subsets

mRNA and miRNA Sequencing

Transcriptomic Signatures of Influenza Vaccine Responses

NCT03603509

May 19, 2019

Analysis Approach. Subjects will be randomly assigned to vaccine type. For all laboratory assays, randomized complete or incomplete block designs that include technical replicates and laboratory controls will be utilized to ensure sample and assay processing are balanced with respect to collection date, vaccine, and sex, keeping specimens from the same subject adjacent to one another. Data will be scrutinized to identify potential biases, batch effects, or failed assays. We will normalize mRNA-sequence data by Conditional Quantile Normalization (CQN), adjusting for library size, gene length, and GC content. Our primary aim is to test the hypotheses that vaccine type (Fluad vs Fluzone) is associated with the change in immune response as measured by hemagglutination inhibition (HAI) Antibody titer. To test this hypothesis, we will use the Wilcoxon Rank Sum test to test for differences between the vaccine types in the change from baseline HAI to Day 28 HAI Ab titers.

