**B. Knowledge Gap—Immune Response Differences to Adjuvanted vs. High-Dose Influenza Vaccines.**

HDFlu contains 60ug HA per influenza strain, and has been the focus of high-quality studies, including a study of 31,989 older individuals ( $\geq 65$  years of age) that demonstrated higher immunogenicity (ratio of GMT 1.8) and 24% greater protection against influenza illness than SDFlu (15ug HA/strain/dose). MF59Flu also induces higher immunogenicity and longer persistence of Ab titers than non-adjuvanted SDFlu. A recent large study in 7,082 individuals ( $\geq 65$  years of age) demonstrated significantly higher immunogenicity ( $p < 0.001$ , seroconversion and HAI GMT) of MF59Flu vaccine compared to SDFlu (particularly against A/H3N2). A single small systems biology study comparing MF59Flu and SDFlu in immunoimmature children (14- to 24-months-old, n=90) identified significantly higher transcriptional responses to MF59Flu and identified early innate response signatures correlated with Day 28 Ab titers. These include M16 (a module associated with TLR and inflammatory signaling); M11 (a module regulating monocyte function); M75 (a module controlling IFN-induced antiviral response); M156 (a module associated with Ab secreting cells); and S3 (a module with genes involved in immunoglobulin production). These genesets and those identified in other systems biology studies of influenza vaccine response will be evaluated for their influence on immune responses to MF59Flu and HDFlu in this proposal.

**The underlying immunologic mechanisms for the improved immunogenicity of MF59Flu and HDFlu are largely unknown for older adults. Our proposal will answer key questions (as illustrated in Figure 1) regarding innate and Th immune responses to these vaccines, the underlying transcriptomic signatures, and their impact on humoral immunity in older adults.** At a minimum, this proposal will fill the knowledge

gap by examining whether the higher immunogenicity of these vaccines is a result of greater activation/suppression of genes/genesets (mRNA and miRNA) previously associated with immune responses to SDFlu, or additional unsuspected genes/genesets controlling immune responses.

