**C. Knowledge Gap—Sex-Based Differences in Immune Responses to Influenza Vaccines.** Studies of **Multiple vaccines** (influenza, yellow fever, MMR, hepatitis A and B, herpes simplex [HSV] 2, rabies, smallpox, and dengue) demonstrate significantly higher Ab responses in females than males, as reported in a series of high-quality papers. Sex-based differences in humoral immune responses are observed prior to puberty, during the reproductive years, and after reproductive senescence, suggesting that sex hormones are not the necessary—or sole—mediators of sex differences in humoral immune responses to vaccines. **Despite significant evidence of immune response differences between the sexes, most vaccine studies do not analyze immune response outcome data by sex.**

Across a cohort of 556 older (ages 50–64) and 558 younger (ages 18–49) subjects, the SDFlu vaccine induced >1.5-fold higher A/H3N2-specific HAI Ab titers in women than men. Similarly, a study of SDFlu and HDFlu vaccine responses in 414 elderly subjects (ages 65–95) demonstrated higher rates of seroconversion in females than in males ( $p<0.05$ ). However, no significant differences in Ab measures were found in cohorts of 494 and 158 older adults after receiving SDFlu, and sex was also not reliably associated with seroprotection and/or Ab titers in children and young adults receiving MF59Flu. **These publications demonstrate inconsistent—and sometimes conflicting—findings regarding sex-based effects on immune responses to influenza vaccine.** Further research is needed, which is a stated priority for NIH research.

Additionally, new vaccines containing the MF59 adjuvant are likely to alter the transcriptomic signatures associated with vaccine responses in elderly populations, and potentially alter the influence of sex on those responses. The current lack of knowledge is a critical barrier to understanding poor vaccine responses in the elderly, and such knowledge is foundational to the future development of new influenza vaccines.

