## Study Design and Methods

### Methods:

#### Subject Recruitment, Enrollment and Screening

We will screen and recruit 400 generally healthy males and females ages 65 and older who meet all inclusion and exclusion criteria and are willing to receive a flu vaccine.

We will also screen and recruit 20 generally healthy males and females ages 18-40 as a control group. These subjects will only have a baseline blood draw (no flu vaccine administration and no follow-study visits).

Eligible subjects who consent and enroll into the study will undergo a baseline blood draw (up to 108 mL) and then be randomly assigned to receive either the MF59 (Fluad) flu vaccine (N=200) or the High Dose (Fluzone) flu vaccine (N=200). Subjects in the control group will undergo the baseline blood draw only (up to 108 mL). They will NOT receive a flu vaccine. The following sections describe the remaining study visits for the subjects who are ages 65 and older.

Subjects will then be asked to come back for three additional blood draws after their flu vaccination: Day 1, Day 8, and Day 28 after vaccination. Each blood draw will be up to 105mL of blood.

Flu vaccination can occur up to 2 weeks after the baseline blood draw. The Day 1 blood draw will occur the following day after vaccination. The Day 8 blood draw will occur 7-10 days after the vaccination. The Day 28 blood draw will occur 25-31 days after vaccination.

During the Baseline visit we will collect patient demographic information, height, weight, BMI, medication history, medical information, and information on alcohol and smoking use. Patients will also be offered the CDC's influenza vaccine-specific Vaccine Information Sheet that is routinely provided to Mayo patients.

During the 3 follow-up visits we will collect weight, medication history and medical information.

Subjects will be remunerated \$40 for each blood draw visit they complete.

We will also mail subjects, roughly a year after participation, 3 different sleep questionnaires as a way to assess sleep hygiene and immune response.

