### **Subject Information**

Target accrual: 420. This includes 400 subjects ages 65 and older (over-recruiting by 10% to account for subject drop-out and insufficient cell recovery from biospecimens) and 20 younger subjects (18-40 years of age) as a control group.

Subject population: Potential participants will be identified through routine clinical appointments, advertising with flyers, brochures, an EMR search to identify mail-merge candidates, and existing lists/databases of individuals interested in being contacted about participation in research studies. Subject recruitment and advertisement will occur on Mayo campus and at various sites off campus (e.g., retirement centers). Permission will be obtained from each location before recruitment begins.

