## Experimental Design:

Below, we briefly describe the assays we will use to monitor/characterize transcriptional changes and specific innate immune response variables at three important time points as informed by other studies and our preliminary data: Baseline (Day 0) and Days 1 and 8 after vaccination. The baseline blood draw allows us to ascertain each subject's pre-existing immune status and provides a baseline upon which to evaluate immunologic changes caused by the vaccine. The Day 1 blood draw allows us to examine early, innate immune responses. The Day 8 sample will be used to characterize plasmablast responses which are directly responsible for humoral immunity and the development of protective Ab titers. The Day 28 blood draw will allow us to examine the peak adaptive immune response.

The assays will be performed either on T- and B-cell depleted PBMCs isolated at each timepoint (for APC immunophenotyping, mRNA, and miRNA) or on T- and B-cell depleted PBMCs stimulated *in vitro* with influenza A/H3N2 (for cytokine/chemokine secretion). This will allow us to capture the *in vivo* and *in vitro* effects of these two vaccines.

**The clinical characterization** of our study subjects will include demographic information, height, weight, medications, and medical conditions that do not meet exclusion criteria. We will also run a CBC to quantify blood leukocyte populations.

**Secreted Cytokine/Chemokine Mediators.** Meso Scale Discovery kits will be used to detect cytokines and chemokines in culture supernatants before and 24 hours after *in vitro* stimulation with influenza A/H3N2.

**Detection of Functional Innate Cell Subsets by Flow Cytometry.** Cellular phenotypes of cells (before and 24 hours after *in vitro* stimulation with influenza virus) will be characterized in Baseline, Day 1, and Day 8 PBMCs by flow cytometry. We will examine the frequency of immune cell types, and characterize their activation by detecting the presence of cell surface markers, co-stimulatory molecules, and activation markers.

**Influenza A/H3N2 Ab Assay.** The HAI Ab assay will be performed using standard protocols. Given the known issues with some A/H3N2 strains, we will utilize influenza antigen matching the vaccine strain and test the antigen for neuraminidase binding to RBCs.

**CMV Serostatus.** CMV Ab titers (IgG) will be measured by multiplex flow-based immunoassay (Bio-Rad).

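### The primary Wilcoxon test on change in HAI titer is valid, but a baseline-adjusted analysis with a GMT ratio and CI would use the same two titers better, and the scale of change is unstated

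*SAP*

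**What the plan says.** The SAP is one paragraph under Analysis Approach. It makes vaccine type and change in HAI titer the primary aim and names one analysis, a "Wilcoxon Rank Sum test to test for differences between the vaccine types in the change from baseline HAI to Day 28 HAI Ab titers". It does not say whether change is a raw difference, a fold rise or a log2 difference. It names no effect estimate, interval, covariate, alpha or sidedness.

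The protocol does not fill these gaps. Under Experimental Design it says "The baseline blood draw allows us to ascertain each subject's pre-existing immune status", but no passage makes baseline HAI a covariate. On the assay it says "The HAI Ab assay will be performed using standard protocols", with no lowest dilution and no value for titers below it. The SAP's laboratory designs "include technical replicates and laboratory controls", without saying how replicates become one titer. The Data Analysis Plan refers to Aim 1 analyses and an Aim 1 power section that are not in the supplied text.

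**The concern.** Three features of the primary comparison could be better at little cost.

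- **Baseline.** A change score fixes the weight on baseline in advance and does not estimate it from the data. When baseline and Day 28 titers are only moderately correlated, that wastes information the trial already collects.
- **Scale.** Ranking does not make the choice harmless, because fold rise is not a monotone function of raw difference. A subject going from 640 to 1280 has +640 but a 2-fold rise; one going from 10 to 320 has +310 but a 32-fold rise. The two scales rank them in opposite order, so two analysts following the SAP could run different tests.
- **Estimate.** A rank-sum p-value alone does not say how much better one vaccine is. The protocol's Background reports earlier HAI results as ratios (a GMT ratio of 1.8 for high dose against standard dose, for example). That is a different contrast, but it shows the scale readers will expect.

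**Working it through.** **Plan's own figures.** No power, SD, correlation or target effect is given for HAI, so there is no power figure to reproduce. The protocol randomises 200 per arm, "over-recruiting by 10% to account for subject drop-out and insufficient cell recovery from biospecimens". Taking 10% off gives 200 × 0.9 = 180 per arm, 360 in all; 360/(1 − 0.10) = 400. The other reading, 400/1.1 = 363.6, makes no practical difference.

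**Variance of the two approaches** (log2 scale, equal variances σ² at both visits, correlation ρ):

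- Change score: 2σ²(1 − ρ). Baseline-adjusted: σ²(1 − ρ²). Ratio: (1 + ρ)/2.
- ρ = 0.3, 0.5, 0.7, 0.8 gives 0.65, 0.75, 0.85, 0.90.
- 360 adjusted subjects are therefore worth 360/0.65 = 554, 480, 424 and 400 analysed by log2 change score.

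**Detectable effect of the planned test** (180 per arm, 80% power, two-sided 5% assumed): √(2/180) × (1.96 + 0.84) = 0.295 SD. Dividing by √(3/π) for the Wilcoxon test gives 0.302 SD of the change. With an assumed SD of 1.8, the SD of log2 change is 1.8√(2(1 − ρ)). This puts the detectable effect at 0.64 log2 for ρ = 0.3, 0.54 for ρ = 0.5 and 0.34 for ρ = 0.8. An effect of 0.5 log2 (1.41-fold) is thus in the range where the choice of method shows.

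**Simulated power.** All inputs are assumptions: 180 per arm, log2 SD 1.8, GMT 40 rising to 160, effect 0.5 log2, doubling dilutions from 1:10 rounded down, below 10 coded 5, 8,000 trials per ρ.

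| Analysis | ρ 0.3 | 0.5 | 0.7 | 0.8 |
|---|---|---|---|---|
| Wilcoxon, raw change | 70% | 78% | 86% | 90% |
| Wilcoxon, log2 change | 58% | 72% | 90% | 97% |
| Linear model, baseline-adjusted | 77% | 84% | 94% | 98% |
| Wilcoxon on baseline-regression residuals | 75% | 82% | 93% | 98% |

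- Linear-model gain over raw change: 7/6/8/8 points. Over log2 change: 18/11/4/1 points (from unrounded power). Repeat runs with separate code agreed within about 3 points.
- Raw and log2 Wilcoxon tests gave different significance verdicts in 20/18/13/10% of trials.
- Type I error was 4.1 to 5.9% (mean 5.0%) over 108 null settings, for all four tests.
- The linear-model GMT ratio averaged 1.41, as simulated. Coverage of its 95% CI was 93.7 to 96.1% over 144 settings with normal residuals.

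**Larger effect.** At 0.8 log2 (1.74-fold) the linear-model gain is at most about 1 point over raw change. Over log2 change it is about 5 points at ρ = 0.3 and little elsewhere. Scale disagreement falls to 0 to 5%.

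**Non-normal residuals.** Over 144 heavy-tailed or skewed settings the linear model was up to 7 points below the planned test, and more than 3 below in 8 to 9% of them. The residual rank test was never more than 1 point below either planned form.

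**Below-limit titers.** About 13% of baselines fall below 1:10 in this setup. Coding them 10 instead of 5 changes the linear-model verdict in 1 to 3% of trials.

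**The case against.** The planned test is valid and robust, and replacing it is a preference. That is right as to validity. A reader might infer that the open scale biases the comparison or inflates type I error. The documents do not support this: allocation is random, each scale holds about 5%, and no passage plans to test both and pick the better.

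The power figures rest on inputs the documents do not give. This stands. The gains belong to intermediate effects and largely vanish at 0.8 log2. The 10% allowance also covers poor cell recovery, which need not affect a serum titer, so 180 per arm may be low.

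The linear model can lose power with non-normal data. This stands too, and it is why the residual rank test is offered as an equal choice of primary.

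It is tempting to settle for defining change as log2 and keeping the unadjusted Wilcoxon test. That is no improvement in power at moderate correlation: it is 70 − 58 = 12 points below raw change at ρ = 0.3 and 78 − 72 = 6 below at ρ = 0.5.

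A reader might also infer that the missing below-limit rule threatens the planned test. Large effects arise only if such titers are excluded, which no passage proposes. With coding 5 or 10, the planned test on raw change alters its verdict in about 1% of trials, and on log2 change in 2 to 6%. The cited assay sources may also state a convention. Finally, the absence of an estimate can be asserted only of the supplied documents, since the Aim 1 analysis text is not among them.

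**Conclusion.** The point holds as a cheap improvement in efficiency and reporting. The primary test as planned is valid, but it uses baseline HAI only through a change of unstated scale, and no estimate or CI is planned in the supplied documents. Baseline adjustment is worth about 5 to 8 points of power over raw change and 1 to 18 over log2 change, allowing for simulation error, if the effect is near 0.5 log2, the log2 SD near 1.8 and the correlation between 0.3 and 0.8. It is worth little if the effect is near 0.8 log2. The case for reporting a GMT ratio with a CI does not depend on these assumptions.

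**What to change.** Before outcome data are seen by arm, state in the SAP:

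- **Primary analysis, baseline-adjusted.** Either a linear model of log2 Day 28 HAI on vaccine type and log2 baseline HAI or, if a rank test is preferred, a Wilcoxon test on the residuals of log2 Day 28 regressed on log2 baseline.
- **Estimate.** In both cases, the adjusted GMT ratio (Fluad/Fluzone) with 95% CI from the linear model.
- **Titer rules.** Titers below the lowest dilution get one fixed value and are not excluded. Say how replicate readings form one titer.
- **Sensitivity.** The Wilcoxon test on change, on both the raw and log2 scales.

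The cost is SAP wording; both titers are already needed for the planned test. The downside is the linear model's possible loss of a few points of power (up to about 7 in the least favourable settings tried), which the residual rank test largely avoids.

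The documents state neither trial status nor blinding. If data by arm have already been seen, choosing a scale now would itself be data-driven. In that case keep the planned Wilcoxon test, use a scale documented beforehand or report both, and label the adjusted model post hoc.
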